- Currently prescribed one of the following adjuvant chemotherapy regimens: (IV 5-fluorouracil [5-FU] / leucovorin [LV], capecitabine, FOLFOX [5-FU, LV, oxaliplatin], CAPOX [capecitabine and oxaliplatin]
 - Patients must have started chemotherapy or plan to start, with planned receipt of the first exercise visit **by the third infusion visit**.
 - Patients receiving FOLFOX chemotherapy are eligible to enroll in the pharmacokinetics sub-study (see section 3.10).
- No planned major surgery anticipated in the intervention period
- Sufficient time to heal from any major surgery to start of intervention, including colostomy reversal (port-a-cath removal excluded)
- Creatinine value < 2 mg/dL
- Approval by either oncologist or surgeon to participate in trial
- Readiness (as determined by the Physical Activity Readiness Questionnaire (PAR-Q) – see Appendix 13.2.2)
 - If there are any indications that home based exercise would be unsafe based on PAR-Q the patient will not be enrolled until confirmation from the patient's treating provider is received via email and/or phone that they are safe to exercise. Provider does not need to be contacted if patient answers 'yes' to 'Is your doctor currently prescribing any medication for your blood pressure or for a heart condition?'
- Ability to understand and the willingness to sign a written informed consent document in English
- Willingness to be randomized

3.4 Exclusion criteria:

- Concurrent actively treated other cancer (except non-melanoma skin cancer, in situ cervical cancer or localized prostate cancer treated with surveillance only)
- Patients with untreated hypertension (> 180 mm Hg systolic or > 100 mm Hg diastolic) appearing in the patient's medical record in the two weeks prior to screening will not be enrolled until confirmation from the patient's treating provider is received via email and/or phone that they are safe to exercise.
- Presence of metastatic disease
- Current strength training ≥ 2 x week for the past 3 or more months
- Patients enrolled in other clinical trials of weight loss, physical activity or dietary interventions are ineligible.

3.5 Inclusion of women and minorities:

We seek to recruit 180 participants with a diagnosis of colon cancer. We will not exclude any participants due to their race and ethnicity. All races are accepted. The distribution of

participants by race and ethnicity is expected to mirror that of the institution's colon cancer patient population.

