3.6 Patient recruitment, registration and randomization requirements:

Prior to initiating recruitment, each study site will obtain separate IRB approval from their respective institutions. Each collaborating site is under their own IRB's purview. Patient recruitment will be specific to each site. At all sites, participants must have the approval of a treating provider in order to participate in the study.

Kaiser Permanente Northern California recruitment:

At KPNC, potentially eligible study participants will be identified using the Electronic Medical Record (EMR) and a pathology database which is updated daily with newly diagnosed cancer cases. Additionally, oncology providers will be made aware of the study and will be asked for patient referrals at each Kaiser facility. Through the EMR, each stage II-III colon cancer patient will be identified close to the time of diagnosis and passively followed through surgery. After confirmation of chemotherapy prescription at the time of first oncology visit, the oncologist will be emailed through our secure internal email system to request approval for study participation for their patient and permission to contact the patient (see Appendix 13.1.1). Once permission is received from the oncologist, we will contact the patient through our secure internal email system and USPS mail, and then by phone to invite them to the study and to screen for eligibility using the above criteria. Contact information (i.e., email, address, phone number) will be identified using the EMR. The MD recruitment email, the participant recruitment email/letter and the recruitment phone script can be found in the Appendix 13.1.

Dana-Farber Cancer Institute recruitment:

Patients will be recruited from the patient populations of the Gastrointestinal Cancer Center clinics at Dana-Farber Cancer Institute. We will utilize multiple active recruitment techniques to maximize participation and generalizability. We will use the following strategies to identify potential participants

- Review of clinic schedules and patient lists for medical oncologists at Dana-Farber to identify patients with Stage II-III colon cancer. HIPAA waiver will be obtained to review these patient lists.
- Education of oncology providers of availability of protocol to encourage oncology providers to identify patients for study staff.
- Tumor registries at Dana-Farber
- Advertisements in patient areas

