Exercise Session	A virtual meeting (except for one in person safety check) or in rare cases if patient does not have video access meeting in person between the exercise professional and the patient. In person will be scheduled on a day when participant has another clinical appointment. In rare instances, an appointment may need to be scheduled on a date and time other than an existing appointment.
Home Exercise Session	Exercise performed by the participant, at home with or without supervision by the cancer exercise professional

Exercise professionals are nationally certified, with expertise working with oncology patients.
Pre-In Person Training Visit Phone Call

1. The intervention begins with a telephone call between the trainer and the participant. The purpose of the call is to:
 - a. Begin to build rapport with the participant
 - b. Give them an overview of what to expect from the exercise training
 - c. Begin behavioral counseling for motivating the participant to adhere to the training regimen
 - d. Provide an opportunity for the trainer to ask about past experience with weight training, any injuries, surgeries or medical conditions that might impact the participant's ability to perform specific exercises.

At Exercise Session 1, the exercise professional will:

1. Teach the participant a warm-up and cool down routine.
 - a. Teach the study specific exercises of the protocol (see Appendix 13.5.3). At the first exercise session, patients will be provided with the handouts for this session using the software SimpleSet Pro that will show pictures and explanations of the movements. Patients will also receive a simple exercise log and protein tracker for the duration of the study.
 - b. A set of adjustable dumbbells and an aerobic step will be shipped to the participant's home. The FORCE Study will cover the cost of purchasing and shipping this equipment.
 - c. Adapt the intensity of the exercises so that the load will fit with the individual physical ability of the patient and will follow the progression scheme in the table below.
 - d. Patients will be instructed to consume one scoop of protein powder, with water, yogurt or milk or other foods about 30 minutes into their meal at 2 meals each day (see

- Appendix 13.6.2). The FORCE Study will cover the cost of purchasing and shipping the protein powder.
- e. Participants will receive a supply of the protein powder. The remainder will be shipped to their homes.

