 - f. For exercise safety purposes, the first exercise session will happen in person, when possible. If not possible, the exercise professional may complete this session virtually by video conferencing. All study supplies (e.g., weights, handouts, exercise logs, protein logs, and protein powder) will be mailed to the participant's home.
2. The exercise and protein log will be used to track the adherence of the patient to the protocol. Patients will be taught to complete the exercise log on the days they perform the exercises at home, along with making any pertinent notes about the exercises and/or how they are feeling. Patients will be taught to complete the protein log daily.
 3. Explain to patients that they should do in-home exercise sessions 2 times weekly until the next Exercise Session with the exercise professional. Patients will complete these exercises alone twice a week. After COVID-19, exercise professionals can offer to work-out virtually with participants once a week.

Table 5. Summary of exercise progression

	Exercise** Session 1	Exercise** Session 2	Exercise** Session 3	Exercise** Session 4	Exercise** Session 5	Exercise** Session 6
SETS	3	3	4	4	5	5
REPS	6	8	8	10	10	10
LOAD*	65%	65%	75%	75%	80%	80%- 85%
REST	30-60 secs	30-60 secs	30-60 secs	30-60 secs	30-60 secs	30-60 secs

*individualized to the patient's strength; **Prior to COVID-19, exercise sessions 1-6 are all in person. After COVID-19, exercise session 1 is in person and sessions 2-6 are virtual.

The exercise professional will meet with the patient for 4-6 Exercise Sessions that will coincide to the degree feasible with their regular infusion sessions. Prior to COVID-19, if scheduling of the Sessions at the clinic is not convenient for the participant, the exercise professional will also be available to conduct these visits at the participant's home. After COVID-19, only Exercise Session 1 is scheduled in person on a day when the participant a clinical appointment, and Sessions 2-6 are conducted virtually via video conferencing. If a participant is not capable of meeting virtually (e.g., lack of technology, internet access or tech skills), the exercise professional will meet the participant in person on the same day as a clinical appointment.

During each follow-up Exercise Session, the exercise professional will:

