4. STUDY MEASUREMENTS

Initial screening will take place via telephone. At the in-person baseline visit, after the patient signs the consent form, s/he will undergo a series of baseline assessments, questionnaires and blood draws as described above. Many of the data collection instruments will be either data entered by a researcher or self-administered by participants into REDCap, which is a secure web application for managing online surveys and databases. The table below provides an overview of the measurements that participants will undergo over the course of the protocol and the timing of these measurements:

Table 7. Measurement Schedule

Measure	Screening	Baseline	Weekly	PK Cohort Only	Post-Intervention Visit ³
Phone screening questions- PA screening and additional questions	X				
PAR-Q	X				
SF-36 ⁴		X			X
Demographics ⁴		X			
Paffenbarger questionnaire		X			X
Physical function tests (balance, gait speed, sit and stand, grip strength)		X			X
Food frequency questionnaire ⁴		X			X
Height, weight, waist and hip circumference		X			X
Whole body DXA		X		X ²	X
Patient-completed side effects questionnaires ⁴		X			X
D3- creatine dilution		X			X
NCI PRO CTCAE			X ¹		
Medical record review for chemotherapy dosing and toxicities			X		
Physical activity and nutrition logs			X		
Inflammatory markers		X			X
Pharmacokinetics (PK)				See section 4.14	
Injury history questionnaire ⁴					X
Intervention follow-up survey					X

¹ At each scheduled intervention visit (for intervention arm) and thereafter by phone or secure web-link every time chemotherapy appointment is scheduled. For U group controls, an RA will administer by phone or secure web-link every time a chemotherapy appointment is scheduled.

² For PK cohort, a DXA scan will also occur at time of 2nd PK draw, at approximately 4 months after initiation of the intervention

³ To be conducted within 2 weeks after last cycle of chemotherapy and end of intervention

⁴ As a result of COVID-19, to reduce in person time participants will complete baseline and post-intervention questionnaires virtually. Study staff will email participants a secure web-link, send them home with paper copies to be mailed back within 3 days, or administer questionnaires over the phone.

4.1 Screening questionnaire:

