Through a screening phone call, we will assess interest in and eligibility for the intervention. This will occur as soon as possible after the patient is scheduled for chemotherapy, ideally before initiation of chemotherapy. We will assess baseline physical activity eligibility by asking a series of physical activity screening questions (see Appendix 13.2.3) in order to ensure eligibility with regard to minutes of physical activity per week (eligibility= not engaging in current strength training ≥ 2 x week for ≥ 3 months). Readiness will be determined using the Physical Activity Readiness Questionnaire (PAR-Q) (see Appendix 13.2.2). This latter survey was specifically designed to screen individuals for whom such unsupervised home-based exercise would be unsafe. These questions will be administered by a trained interviewer and those not meeting the eligibility qualifications (either already exercise too much or unsafe to exercise without supervision) will be reviewed by their treating oncologist and/or the study oncologist for advice on suitability of exercise intervention participation. We will also ask whether the individual has any planned major surgeries or is currently enrolled in other weight loss, physical activity or dietary studies (see Appendix 13.2.4). A researcher will record all screening question responses in an online REDCap form.

4.2 Demographic and health information:

Participants will be asked to complete a brief standardized survey regarding gender, marital status, household size, race and ethnicity, educational level, occupational status. In addition, cancer registry data and EMR will be reviewed for information on prognostic factors, including disease stage, nodal status, histologic grade, surgical procedures, and treatment medical history/comorbidities, cardiometabolic risk factors, including blood pressure. See Appendix 13.4.1. A researcher will record all relevant health information in an online REDCap form. Participants will complete an online REDCap survey about demographic information.

4.3 Medical outcomes study 36-Item, short form (SF-36):

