Details of each patient's health history, including medical imaging, comorbidities and colon cancer diagnosis and treatment details will be extracted from the EMR. In addition, laboratory and clinical data about the colon cancer tumor marker Carcinoembryonic Antigen (CEA) and cardiometabolic risk factors blood glucose, lipids, blood pressure and medication usage conditions will be extracted from the EMR. See Appendix 13.2.1. A researcher will record all relevant medical variables in an online REDCap form. In addition, CT scans will be obtained from the participant's medical record. KP scans will be stripped of PHI and analyzed at DOR. Penn State and DFCI scans will be stripped of PHI and transmitted directly to DOR via SFT. CT scan closest to the date of diagnosis but before chemotherapy will be colored using TomoVision sliceOmatic software to determine body composition, including muscle attenuation.

4.10 Body composition and body size:

At the baseline visit and at the follow-up visit, a DXA scan to assess body composition will be performed (see Appendix 13.8.2). All DXA scans will be performed in the total body scanning mode. A third scan will take place after 4 months for the subset of people participating in the PK study to correspond to timing of the 2nd PK blood draws.

At the baseline visit and at the follow-up visit, d3-creatine dilution will be used to accurately assess total body skeletal muscle mass (see Appendix 13.8.3).

Height and weight will be assessed using a scale mounted stadiometer and digital scale (or per institutional clinic standards) to the nearest 0.1 cm and 0.1 kg. Waist circumference and hip

circumferences will be measured at standardized landmark with participants dressed in light indoor clothing without shoes. Height will be assessed at baseline only. A researcher will record anthropometric measurements in an online REDCap form. See Appendix 13.8.1.

Because of COVID-19, if a participant doesn't feel comfortable with study staff touching him/her for waist or hip circumference measures, the study staff can teach the participant how to self-measure while observing and recording results in REDCap.

4.11 Dose reductions/delays and early discontinuation of treatment:

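### Read literally, Protocol 3.4 asks for blood-pressure-specific provider confirmation only in untreated patients, so a treated patient with the same charted reading and no other PAR-Q flag needs none

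*Protocol*

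**What the plan says.** Four parts of the Protocol bear on this point.

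- **Section 3.4 (exclusion criteria).** The blood-pressure criterion covers "Patients with untreated hypertension (> 180 mm Hg systolic or > 100 mm Hg diastolic", with the reading taken from the medical record in the two weeks before screening. Either limit is enough. The criterion works as a hold and not as a ban: enrolment waits until the treating provider confirms by email or phone that exercise is safe.
- **Section 3.3 (inclusion criteria).** Any PAR-Q sign that home exercise would be unsafe triggers the same kind of hold, with one exception: "Provider does not need to be contacted if patient answers 'yes' to 'Is your doctor currently prescribing any medication for your blood pressure". The same item also asks about heart medication.
- **Sections 3.3 and 3.6 (general approval).** An oncologist or surgeon must approve participation, and 3.6 adds: "At all sites, participants must have the approval of a treating provider in order to participate in the study". Neither requirement mentions blood pressure.
- **Section 4.9 (medical record review).** It states that "cardiometabolic risk factors blood glucose, lipids, blood pressure and medication usage conditions will be extracted from the EMR" and points to Appendix 13.2.1, which the appendix list names as the Screening Eligibility Form. No threshold or action is attached to these data in the text.

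**The concern.** By adding a hold in 3.4, the protocol itself judges that general approval is not enough when a recent reading is above 180 systolic or 100 diastolic. It then limits that hold to patients who are not on treatment. The protocol gives no reason why the same reading should need less attention in a patient who has it despite medication. The waiver in 3.3 points the same way, because the PAR-Q item that identifies treated patients is the one item that does not prompt a call.

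What is at stake is a safety check before progressive resistance training. Table 5 rises to 5 sets at 80% to 85% load, individualized to strength. On the home sessions, 3.8 says "Patients will complete these exercises alone twice a week", although after COVID-19 a weekly virtual work-out can be offered. The point concerns consistent participant protection. It does not touch the estimation of the treatment effect.

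**Working it through.** No formula applies, and the plan gives no figure to reproduce. The check is to follow patients with the same chart reading through the text. Take 190/105 as an illustration, recorded within two weeks before screening.

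| Patient | 3.4 hold | 3.3 PAR-Q hold | General approval (3.3, 3.6) | Reading-specific confirmations required |
|---|---|---|---|---|
| (a) Untreated, no PAR-Q flag | Applies | Not triggered | Required | 1 |
| (b) Treated, no PAR-Q flag except the medication item | Does not apply as worded | Contact waived | Required | 0 |
| (c) Treated, with another PAR-Q sign that exercise is unsafe | Does not apply as worded | Applies | Required | 0 (but a provider confirmation is required for the PAR-Q flag) |

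Case (b) is the gap. The next step is to see whether another part of the protocol body closes it.

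1. **Section 4.1.** People who do not meet the eligibility qualifications "will be reviewed by their treating oncologist and/or the study oncologist for advice on suitability of exercise intervention participation". Patient (b) fails no stated qualification because of the reading, so this review is not triggered by it.
2. **Table 7.** It lists no blood-pressure measurement at any visit. Its weekly chart review is described as "Medical record review for chemotherapy dosing and toxicities", which is a different purpose.
3. **Section 4.9.** Blood pressure and medication use are extracted, but as study data with no stated limit or response.
4. **Section 3.8, trainer's introductory call.** It asks about "any injuries, surgeries or medical conditions that might impact" the participant's ability to do particular exercises. Hypertension could come up, but no reading is looked at.
5. **Section 7.** The study team or clinicians can remove a patient when continuing is judged unsafe. Nothing there is prompted by a reading.
6. **Timing of general approval.** At Kaiser Permanente, expected to enrol about 115 of 180, the oncologist is asked for approval before the patient is contacted and screened (3.6). That request is not described as involving a review of blood pressure.

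None of these sections ties an action to a blood-pressure reading in a treated patient.

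**The case against.** The strongest reply is that everything turns on one undefined word. *Untreated* may have been meant as *uncontrolled*, and a coordinator looking at the numeric limits and the two-week chart window might apply it that way. If the word was deliberate, there is a possible rationale: a treated patient already has a prescriber managing the pressure. The first part stands as a real possibility, and it makes this partly a matter of wording. The second is plausible, but the protocol does not state it, and a recent reading above the limit despite medication is not obviously reassuring.

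A second reply is that the gap may be closed in forms that cannot be seen here. Section 4.9 links blood pressure and medication use to the Screening Eligibility Form, and only one PAR-Q item is waived. Neither form is reproduced. This stands: a further check cannot be ruled out, so it cannot be said that a site would in fact enrol such a patient without a call.

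A third reply is that clinical oversight is already substantial: general approval, the trainer's call, individualized load, an in-person first session when possible, weekly contact, removal on safety grounds and a monitoring board. These are real safeguards, but none is tied to a reading. The untreated patient has them all too, and 3.4 still asks for more.

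A reader might go further and infer that treated hypertensive patients enter with no medical clearance, or that the waiver forbids contacting the provider. The documents support neither. Approval is required of everyone, and the waiver only says that contact is not needed.

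**Conclusion.** The point holds as a gap in the protocol body. For the same charted reading above either limit, one reading-specific confirmation is required if the patient is untreated and none if the patient is treated with no other PAR-Q flag. This rests on reading *untreated* literally and on the two unreproduced forms adding no check of their own.

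The size of the affected group cannot be estimated. The documents give no share of patients who are treated, have such a reading in the two-week window and have no other PAR-Q flag. That is a joint condition, and the number may be small. A reader might want to turn it into an expected count or a probability of harm, but nothing in the documents anchors either. What is missing is a confirmation, which a provider might well have given.

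No endpoint, analysis or power figure is affected. SAP 2.1 reports 183 participants already randomized (92 to resistance training and 91 to usual care), so a change to the enrolment rule cannot protect them. The point is a cheap correction to a stated safety rule. It is not a reason to doubt the trial's results.

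**What to change.** - **Section 3.4:** delete the word *untreated*, so that any charted reading above either limit in the existing two-week window triggers the existing email or phone confirmation, whether or not the patient is on treatment. If *uncontrolled* was intended, the deletion achieves that too.
- **Section 3.3:** add one sentence saying that the waiver for the medication item does not apply when such a reading is on file.

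The limits themselves are for the sponsor's clinicians and need not change.

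The cost is a few extra provider contacts and an occasional short delay to the first session. The delay deserves some attention because 3.3 requires the first exercise visit by the third infusion visit. Nobody is newly barred, since 3.4 is a hold pending confirmation. No new measurement is needed, because blood pressure and medication use are already taken from the EMR under 4.9.

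With randomization reported, the edit is for further use of the protocol. For the present trial, the useful step is to check the Screening Eligibility Form and PAR-Q for an existing safeguard, and to count from the extracted EMR data how many treated participants had a reading above either limit in the window.
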